## **Economic evaluation measures**

*Please refer to the detailed economic evaluation information sheet attached if you require more information.*

### **Methods**

A trial- and model-based economic evaluation will be conducted from the public sector perspective, which will include the costs and consequences to the: local authority, NHS and PSS, and local authority leisure centre. Results from all analyses will be reported in the form of an incremental cost-effectiveness ratio. Firstly, a cost-utility analysis will be carried out with the results being presented as cost per quality adjusted life year. Secondly, a cost-effectiveness analysis will be carried out with the results being presented as cost per active participant. Lastly, a cost-consequence analysis will be conducted from a broader perspective, which will highlight relevant public sector and participant costs and consequences. More specifically, the main analysis will be done by exploring the costs and effects over a lifetime horizon, using a decision-analytic model. All costs and effects over the lifetime horizon will be discounted at a rate of 3.5% as recommended in the NICE reference case (NICE, 2017). The 6-month effectiveness data for change in physical activity level, as well as published secondary data sources on change in disease state will be input into the model. The extrapolated analysis will aim to estimate the relative risk of participants being in one of the following six health states 10 years after the intervention: healthy, dead, has had a stroke, has coronary heart disease (CHD), or has type 2 diabetes (T2D). The 10-year duration of effect period is a conservative approach, which has been based on a recently published study (Campbell et al. 2015) that was identified in the systematic review. All

epidemiological data along with additional published secondary data on the life expectancy, health-related quality of life and treatment costs associated with each of the six health states will be input into a Markov Model. Uncertainty will be assessed through deterministic and probability sensitivity analyses.

#### ***Data collection***

**Resource use measures.** Direct costs to the local authority will be measured, these will include the annual cost of operating the intervention, and the set up costs. A breakdown of these costs will be requested from the local authority. Any additional costs will be captured through a questionnaire completed by key staff coordinating the Exercise Referral Scheme at the local authority, local authority leisure centre, and research institute delivering the training. Indirect short-term cost savings to the NHS and PSS will be captured via health care utilisation questionnaires completed by the participants at baseline, and at 6 months follow up. The long-term indirect cost savings to the NHS and PSS through a reduction in coronary heart disease, stroke and type 2 diabetes will be sources from secondary data. A short telephone interview will be conducted with the leisure centre manager to identify whether the centre experienced a loss in revenue as a result of providing the Exercise Referral Scheme. Participant out of pocket and productivity costs will be captured through self-reported questionnaires at baseline, 12 weeks, and 6 months from baseline. All questionnaires and telephone interview questions are adapted from validated measurement tools from the Database of Instruments for Resource Use Measurement. Apart from room hire, primary data will not be collected for common overhead operating costs, such as lighting and heating; however, these costs will be explored in the sensitivity analysis, for instance by estimating the hours of the intervention and increasing the salary rates of staff by 10% to include overheads. Unit cost prices will be sources from secondary sources.

**bEconomic evaluation measures (attached: located at the end of Booklet 2):**

**Health-related quality of life measure.** Participants' change in health-related quality of life (HRQoL) will be measured at baseline, 12 weeks, and 6 months. The EQ-5D will be used, this is a validated tool for measuring HRQoL. This tool has been applied successfully in a recent UK trial-based economic evaluation of exercise referral schemes (Edwards et al. 2013).

**Intervention operating and set up costs.** Captured via telephone interview with Exercise Referral Scheme Personnel from (organisation e.g. local authority/ leisure centre/ research institute; questions adapted from validated questionnaire).

**Loss in revenue costs.** Captured via telephone interview with leisure centre manager and/or coordinators (questions have been used in previous research).

**Patient costs.** Captured via patient questionnaire during lab testing (questions adapted from validated questionnaire).

**Patient Health care utilisation costs.** Captured via questionnaire (questions adapted from validated questionnaire).

### **Patient procedure**

*LJMU lab-based measures.* Written informed consent will be gained prior to the commencement of testing, when patients arrive at LJMU for baseline testing with a researcher. Patients will need to be rested for 20 minutes prior to initiation of the ultrasound techniques. During this period, demographic data will be collected in addition to information about PA levels, mental wellbeing, diet, smoking and alcohol habits, psychological questionnaires and economic-related questions (~30 minutes; see attached Booklet 1 and Booklet 2). Ultrasound measures will then be conducted (FMD and CAR): 25 minutes. A 15ml blood sample will be taken from the antecubital fossa (5 minutes). The participant will then be able to drink and eat, if they wish, prior to completing a sub-maximal fitness test (20 minutes). The patient will then be informed about the accelerometry protocol and given the Actigraph monitor with accompanying diary to be completed over a seven-day period (5 minutes). For the ERS arms, the accelerometer and accompanying diary will be returned to the ERP when the patient attends their referral induction at Centre A or Centre B to begin their programme. The control group participants will return the monitors to LJMU in person or by pre-paid mail. The expected period to complete baseline testing is ~90-120-minutes.

Lab based testing will be repeated at week 12 as per the protocol for baseline data collection described above. At 6 months from baseline, participants will be sent (by mail) a questionnaire pack (booklet 2) and an activity monitor. These will be returned via pre-paid mail or as otherwise organised with the researcher.

### **Protocol for incidental disclosures or abnormal test results**

*Disclosure of unhealthy lifestyle* – Whilst it is not deemed appropriate for researchers to pass on lifestyle information disclosed in confidence, or to provide individual advice, it is recognised that the research team have a responsibility to provide evidence-based information to allow patients to make informed decisions about their health. Therefore, after completing their baseline assessments at LJMU participants will each be given a simple information sheet that outlines the recommended guidance on PA and diet as well as risks associated with smoking and alcohol. On the sheet participants will be signposted to relevant government

websites for further information and will be advised to contact their GP if they have any concerns about their own lifestyle.

*Abnormal test results.*

The laboratory-based testing is not diagnostic in nature and is therefore not likely to find anything alarming. However, if any abnormal blood results (analysed following week 12 testing) are identified, the researcher will write to the individual participant and ask them to see their GP. Refer to attached patient letter.

**Analyses**

Statistical analysis of the primary and secondary outcomes will be conducted using linear mixed models in SPSS Statistics Version 23 (SPSS Inc., IBM Corp., Armonk, NY), with alpha levels set at  $P < .05$ . The models will be used to assess the impact of treatment (co-developed ERS, usual care ERS, and no treatment control), time (baseline and post-tests), and Group  $\times$  Time interactions. Mixed models are robust to the biases of missing data and provide appropriate balance of Type 1 and Type 2 errors. Mixed-model analyses are consistent with the intention-to-treat principle, assuming the data are missing at random. Appropriate variables including baseline values will be included as covariates in the models. The data will be screened for skewness and kurtosis prior to commencing any analyses. Magnitude-based inferences will be used to investigate 'clinical meaningfulness' of results (Batterham and Hopkins 2006).

Focus groups and interviews will be recorded and transcribed verbatim (where they will be anonymised). They will then be analysed using NVivo electronic software using a thematic approach to allow common themes to arise from the data collected. Members of the research team will review the data independently and meet to reflect on the emerging themes, discuss rationale for coding decisions, areas of disagreement and theoretical concepts that emerge.

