### **Objectives:**

- To investigate the relative effectiveness (for improving cardiorespiratory fitness at 12 weeks) and cost-effectiveness (PA levels at 6 months) of two delivery modes of ERS (1. co-developed physical activity referral scheme; 2. standard ERS)
- To explore who each intervention reaches, patient adherence levels, fidelity of intervention delivery and acceptability of the intervention to patients and staff.

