## Sample size estimation

### *Between-group effects (intervention vs usual care)*

Required sample size was estimated by using effect sizes of a previous pilot study that demonstrated a mean change in CRF  $3.6 \pm 3.2 \text{ ml.kg.min}^{-2}$  (REF 16/WA/0231) and existing epidemiological evidence. A change in cardiorespiratory fitness of  $3.5 \text{ ml.kg.min}^{-2}$  has been deemed clinically meaningful with an associated reduction in all-cause mortality (13%) and cardiovascular disease risk (15%; Lee et al., 2010). Yet, it has also been demonstrated that small increases in fitness (Males:  $0.5 \text{ ml.kg.min}^{-2}$ ; Females  $1.0 \text{ ml.kg.min}^{-2}$ ) are associated with significant reductions in clustered-cardiometabolic risk in at-risk individuals (Simmons et al., 2008).

Therefore, we decided a moderate-large effect size (based on pilot baseline CRF SD of  $3.2 \text{ ml.kg.min}^{-2}$  equivalent to a change of  $1.98 \text{ ml.kg.min}^{-2}$ , would be clinically meaningful. This is between the clinically meaningful change of 3.5 units reported by Lee et al. (2010) and the smaller increases of 0.5 to 1 unit reported by Simmons et al. (2008) in at-risk individuals. Thus, to detect a difference of 1.98 units ( $\text{ml.kg.min}^{-2}$ ) between groups, it was estimated that a total sample of 84 would be needed ( $f=0.25$ ,  $p=0.05$ , power = 0.8). Factoring for dropout witnessed in the pilot study (40%) this yields a sample of 140 patients (70 per ERS arm).

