### *Between-group effects (ERS arms vs no treatment control)*

It is estimated that a larger effect size would occur between the ERS arms and the no treatment control, it was therefore decided we did not need to recruit as many participants. To identify a difference of 3.2 units ( $\text{ml.kg.min}^{-2}$ ; 0.3 units smaller than the within-subjects change seen in the previous pilot for fitness to allow for some variance) between the ERS arms and a no treatment control arm a sample of 17 would be required ( $f=0.5$ ,  $p=0.05$ , power = 0.8). Factoring for dropout witnessed in the pilot study (40%) this yields a sample of 30 patients for the no treatment control arm.

In summary, the study will aim to recruit 70 patients for the intervention condition, 70 for the usual care condition and 30 for the no treatment control.

*ERPs.* All ERPs responsible for delivering the ERS at Centre A (n=4-5) and Centre B (n=2-3) will be invited to take part.

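### The terms written into the analysis model do not deliver the scheme-versus-scheme week-12 fitness difference that the objective asks for and the sample size is built on

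*Combined protocol and SAP*

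**What the plan says.** The Objectives section sets one effectiveness question: "To investigate the relative effectiveness (for improving cardiorespiratory fitness at 12 weeks". The same bullet then names the economic outcome together with the arms to be compared: "cost-effectiveness (PA levels at 6 months) of two delivery modes of ERS (1. co-developed physical activity referral scheme; 2. standard ERS". The no-treatment arm does not appear in it.

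The sample size section has two parts. The first is headed "Between-group effects (intervention vs usual care" and reads "Thus, to detect a difference of 1.98 units" and "it was estimated that a total sample of 84 would be needed". The second deals with the no-treatment arm separately: "It is estimated that a larger effect size would occur between the ERS arms and the no treatment control", and "To identify a difference of 3.2 units".

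Under Outcome measures, CRF is collected at baseline and week 12 only.

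The Analyses section gives one model statement for all primary and secondary outcomes: "The models will be used to assess the impact of treatment (co-developed ERS, usual care ERS, and no treatment control", then time (baseline and post-tests) and Group × Time, at P < .05. It also enters baseline values as covariates and adds magnitude-based inferences. Neither this section nor any other says which outcome is primary, which pair of arms is compared, or which coefficient carries the conclusion.

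**The concern.** Three results could be reported as the treatment effect on CRF: a three-level main effect, a three-level interaction, or a baseline-adjusted week-12 difference. They answer different questions.

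- A three-level test responds to any difference among the arms, including ERS against no treatment, where the plan expects the larger effect. A significant result need not mean that the co-developed scheme beats usual care.
- A main effect over time includes the baseline visit, when no scheme has yet acted.
- Using baseline both as an outcome row and as a covariate makes the two rows of one person depend on each other in a way that the usual model does not represent.

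What is at stake is which result is presented as the answer to the objective, and whether its estimate and standard error are right.

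**Working it through.** **Inputs.** Difference 1.98, SD 3.2, 84 evaluable (42 per ERS arm), 40% dropout, 17 evaluable and 30 recruited controls, ERS-control difference 3.2, pilot change 3.6: all from the sample size section. Evaluable controls are 17, or 30 × 0.6 = 18. Two-sided 5% is assumed, as the plan does not state sidedness.

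**1. The plan's own figure.** n per arm = 2(1.960 + 0.842)² × 3.2² / 1.98² = 41.0, rounded up to 42. The noncentral t gives power 0.800 at 42 per arm and 0.790 at 41. So 2 × 42 = 84, and 84 / 0.6 = 140. Both figures are reproduced, and they are figures for the two-scheme contrast. (The stated f = 0.25 does not match 1.98 / 3.2 / 2 = 0.309; that is a separate issue.)

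**2. Three-arm test when the schemes are identical.** One-way F, complete data, no covariates. If both schemes lie D above control, the noncentrality is λ = [84 × n_c / (84 + n_c)] × D² / 3.2².

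| D | n_c | λ | Probability of significance |
|---|---|---|---|
| 3.2 | 17 | 14.14 | 0.923 |
| 3.2 | 18 | 14.82 | 0.935 |
| 1.62 | 17 | 3.62 | 0.370 |
| 1.62 | 18 | 3.80 | 0.386 |

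D = 3.2 is one reading of the plan's control comparison; D = 1.62 is 3.6 − 1.98. In every row the true scheme-versus-scheme difference is zero.

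**3. Treatment main effect over both visits.** With equal baselines, the scheme difference is 0 at baseline and 1.98 at week 12. The average is (0 + 1.98) / 2 = 0.99, half the quantity in the objective.

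**4. Baseline used twice.** Assume equal variance σ² at both visits, baseline to week-12 correlation ρ, n per arm, and a random-intercept model (the plan states no covariance structure).

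- The slope on the baseline covariate is 1 in the baseline rows and ρ in the week-12 rows, so the common slope is (1 + ρ)/2.
- The residual covariance within a person is then −σ²(1 − ρ)²/4. It is negative, so the random-intercept variance sits at its bound of zero and the rows are treated as independent.
- The mean residual variance is σ²(1 − ρ)(3 + ρ)/4, so the model takes the variance of the scheme-versus-scheme Group × Time estimate to be σ²(1 − ρ)(3 + ρ)/n.
- The true variance of a difference in change is 4σ²(1 − ρ)/n.
- The ratio of model SE to true SE is √[(3 + ρ)/4]: 0.908 at ρ = 0.3, 0.935 at 0.5 and 0.981 at 0.85.
- The false-positive rate, 2[1 − Φ(1.96 × ratio)], is 7.5%, 6.7% and 5.4%. Simulation with 42 per arm gives 7.3% falling to 5.7% over ρ = 0.3 to 0.85.

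Under the same conditions, analysis of covariance (ANCOVA) with baseline as covariate only recovers 1.98 at close to the nominal error rate.

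**5. Would a gate matter?** Suppose the contrast were read only after a significant three-arm test, with a true 1.98 between the schemes and control lowest, as the plan expects. With the schemes 3.2 and 1.22 above control, three-arm power is 0.93-0.94 and gated power for the contrast is 0.79, against 0.80 ungated. With 3.6 and 1.62 above control the figures are 0.97 and 0.80. The loss is about 1 point or less.

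**The case against.** The strongest reply is that the intended contrast is plain. The objective names the two schemes, the outcome and the week; the sample size is headed with that pair; and CRF has no other follow-up visit. A three-level factor in a mixed model also yields pairwise estimates, and the Analyses section never says that an overall F test decides anything. All of this stands. It makes the point a gap in specification, not a contradiction.

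A reader might infer that the trial loses power because the three-arm test acts as a gate. Such a calculation gives 73% if control equals usual care and 69% if control lies midway between the schemes. The documents do not support this. No gate is stated, and both placements run against the plan's expectation that the larger difference is against control.

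A reader might also infer that reading the contrast after the three-arm test inflates false claims that one scheme beats the other. It does not: at ERS-control differences of 0, 1.62 and 3.2 the rates are 2.5%, 4.3% and 5.0%. The excess in step 4 comes from using baseline twice, not from the order of testing. This says nothing about multiplicity across the many other outcomes.

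Finally, a mixed model was chosen partly for missing data, and baseline as covariate only gives up that form for CRF. That is a real cost, listed under the fix.

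**Conclusion.** The concern holds as a specification gap that affects the estimate. The contrast can be inferred from the Objectives and sample size sections, but the written model terms do not deliver it.

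- A significant three-arm result says little about the objective: it occurs in about 92-93% of trials with identical schemes if both are 3.2 above control, and in 37-39% if both are 1.62 above.
- A main effect over both visits halves the week-12 difference.
- The scheme-versus-scheme part of Group × Time does target the difference in change, but using baseline twice can understate its standard error, with about 6-7% false positives.

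The first result rests on a one-way simplification at SD 3.2. The second rests on equal baselines. The third rests on assumed correlations of 0.3-0.85 and a random-intercept structure. Neither a gating loss nor an error in the 84 follows from this point. Severity: minor to should-fix.

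**What to change.** In the Analyses section:

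- State that the primary result is the baseline-adjusted difference in week-12 CRF, intervention minus usual care, tested two-sided at 5% and reported with a 95% CI, and not conditional on the three-arm test.
- Use baseline CRF as a covariate only. With one post-baseline CRF value this is ANCOVA, and the text should say so.
- Report each ERS arm against control, and the other outcomes, as secondary. Keep 6-month physical activity for the cost-effectiveness objective.
- State that magnitude-based inferences do not override the primary result.
- Report difference in change as a sensitivity analysis. Allocation is not random, so with unequal baselines it can differ from ANCOVA.

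**Cost.** Text only; the numbers stay at 84 evaluable and 140 recruited. People without a week-12 test do not contribute to the primary estimate, but the 84 already excludes them. Power of 80% and a CI half-width of 1.989 × 3.2 × √(2/42) = 1.39 are for the unadjusted comparison. If 3.2 is the raw SD, adjustment multiplies the half-width by about √(1 − ρ²), giving 1.20 at ρ = 0.5 and 0.99 at ρ = 0.7 (assumed values). The sample size section attaches 3.2 both to the pilot change and to the baseline SD, so this gain is not assured. The change does not address confounding from non-random allocation.

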#### **Conditions**

##### ***Intervention (Centre A)***

[figure not shown]
Both the co-developed scheme and standard ERS offer subsidised access to a fitness centre for 12 weeks. However, in addition to this the co-developed intervention (centre A) will offer:

- more physical activity options that include both daily opportunities to increase PA and activities available at the fitness centre;
- more individual progress meetings, during which the GP exercise referral practitioner will provide behaviour change support (Week 0, 4, 8, 12 and 18); and
- more efforts to refer patients to optional additional support from a 'Health Trainer' service qualified to provide advice on multiple health-related behaviours.

These adaptations are in line with the current NICE guidelines as well as a local evaluation study that fed into the development of the scheme. The aim of the co-developed ERS is a person-centred approach to improve overall well-being and quality of life through PA. As the intervention is drawing on an existing scheme, delivered/guided by qualified ERPs, and has been developed by a multidisciplinary stakeholder group involved with the existing scheme, it is deemed that there are no additional risks to the users compared to the existing

scheme in operation. The key aspect of the intervention is that the participant has choice but is supported through the process.

It was found during the pilot study that some patients were referred inappropriately to the ERS who were already active or were seeking subsidised access to certain activities (e.g. swimming) without a need for additional behaviour change support. In an attempt to provide more targeted support, patient eligibility for the ERS will be explored through the patient-centred induction. If it is deemed by both the instructor and patient that the intensive 18-week intervention is not the most appropriate for the patient's needs, alternative options will be offered (see figure 1). Since this study aims to investigate the real-world effectiveness of an ERS that is tailored to patient needs, patients referred to the ERS at Centre A who opt not to take part in the 18-week intervention will remain in the research study (i.e. an intention to treat approach).

**Figure 1.** Co-developed referral scheme that will run at Centre A (intervention centre).

[figure not shown]

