### ***Usual care (Centre B)***

The usual care arm will follow a standard ERS model of 12-week access to a *Lifestyles* fitness centre. Patients referred from a health professional (GP, physiotherapist, nurse etc.) will meet an ERP at the leisure centre for an initial induction (week 1). A personalised exercise intervention will be provided to the patient based on their referral reason/health condition. The patient will have 12 weeks of subsidised access to the gymnasium and group classes. This system is already in place and is considered standard exercise referral care for the local area.

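### The sample size and planned model make no allowance for clustering by the six to eight practitioners who deliver the two schemes, so the stated 80% power and 5% error rate hold only if patients of the same practitioner are uncorrelated

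*Combined protocol and SAP*

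**What the plan says.** **Who delivers.** The sample size section closes with the staffing: "All ERPs responsible for delivering the ERS at Centre A (n=4-5) and Centre B (n=2-3) will be invited to take part". That is six to eight people for both active arms.

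**What they deliver.** Among the additions at Centre A are "more individual progress meetings, during which the GP exercise referral practitioner will provide behaviour change support", at weeks 0, 4, 8, 12 and 18. At Centre B patients "will meet an ERP at the leisure centre for an initial induction (week 1") and receive a personalised exercise programme. Under Process Measures, Centre B consultations are recorded at induction and 12 weeks only.

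**Sample size.** Under Between-group effects (intervention vs usual care), the target is a between-group difference of 1.98 units and "it was estimated that a total sample of 84 would be needed"; after allowance for 40% dropout, "this yields a sample of 140 patients (70 per ERS arm"). No ICC or design effect is given.

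**Model.** The Analyses section names linear mixed models and says: "The models will be used to assess the impact of treatment (co-developed ERS, usual care ERS, and no treatment control), time (baseline and post-tests"), followed by Group x Time interactions and unspecified appropriate covariates including baseline values. It names no random effect and no practitioner term.

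**The concern.** When a few practitioners each treat many patients, differences between practitioners enter the arm mean and do not average out as patients are added. A standard error that counts patients only leaves this component out. Intervals for the scheme contrast are then too narrow, P < .05 is reached too often, and the planned power is too high.

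The protocol itself gives reason to think practitioners may differ. It audio-records a sample of consultations and codes them for needs-supportive communication, and it asks patients how supportive they find their instructors. An analysis plan that allows for no practitioner effect on outcome sits uneasily with that.

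Practical timing also matters: if nobody records which ERP saw which patient during delivery, the question may be hard to answer later.

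**Working it through.** **Inputs from the documents.** Difference 1.98; SD 3.2; alpha 0.05; power 0.80; 84 evaluable, so 42 per arm; 140 recruited, so 70 per arm; ERPs 4-5 (A) and 2-3 (B).

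**Assumptions, not in the documents.** ICC of 0.01, 0.05 or 0.10 for change in fitness (or the baseline-adjusted week-12 value); one ERP per patient; equal caseloads within a centre.

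**Step 1: reproduce the plan's figure.** d = 1.98/3.2 = 0.619. A two-sided two-sample t-test with independent patients needs 42 per arm, so 84; 84/0.6 = 140. Both figures reproduce with no design effect. The f = 0.25 printed beside them does not: it would need 128. That is a separate inconsistency; the 84 matches 1.98/3.2 (f = 0.309).

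**Step 2: caseloads.** With 42 per arm, Centre A has 42/5 = 8.4 to 42/4 = 10.5 patients per ERP, and Centre B has 42/3 = 14 to 42/2 = 21.

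**Step 3: design effect.** Per arm, DE = 1 + (m - 1) x ICC, with m the caseload. With equal arms, the contrast takes the mean of the two. At ICC 0.05:

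- 5 and 3 ERPs: (1.370 + 1.650)/2 = 1.510
- 4 and 2 ERPs: (1.475 + 2.000)/2 = 1.738

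**Step 4: error rate and power.** The false-positive rate of the unadjusted test is 2 x [1 - Phi(1.96/sqrt(DE))]. Power allowing for clustering is Phi(1.98/SE - 1.96), with SE = 3.2 x sqrt(2 x DE/n). At ICC 0.05 and 5 and 3 ERPs, SE = 3.2 x sqrt(2 x 1.510/42) = 0.858, 1.98/0.858 = 2.31, and power is 64%.

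Each range below runs from 5 and 3 ERPs to 4 and 2 ERPs.

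| Per arm | ICC at A / B | DE | False-positive rate, formula | Simulated t-test | Power for 1.98 |
|---|---|---|---|---|---|
| 42 | 0 / 0 | 1 | 5.0% | - | 81% |
| 42 | 0.01 / 0.01 | 1.10-1.15 | 6.2-6.7% | 6.1-6.7% | 77-75% |
| 42 | 0.05 / 0.05 | 1.51-1.74 | 11.1-13.7% | 11.2-14.0% | 64-58% |
| 42 | 0.10 / 0.10 | 2.02-2.48 | 16.8-21.3% | 17.1-21.8% | 51-44% |
| 42 | 0.05 / 0 | 1.19-1.24 | 7.2-7.8% | 7.1-7.8% | 74-72% |
| 70 | 0.05 / 0.05 | 1.88-2.26 | 15.3-19.3% | 15.6-19.8% | 76-68% |

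The 81% in the first row is the normal approximation to the plan's 80%.

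**Step 5: small-sample penalty.** If the practitioner variance is estimated from the data, the test has roughly 5 + 3 - 2 = 6 or 4 + 2 - 2 = 4 degrees of freedom. At ICC 0.05 and 42 per arm, a noncentral t calculation gives power of 49% or 38%. A simulated random-effect test with Satterthwaite degrees of freedom gives 48% or 35%.

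**The case against.** **The ICC is unknown.** Nothing in the documents makes 0.05 likelier than 0.01 for a cycle-test fitness outcome, and at 0.01 the test is close to nominal. This stands. A reader might infer that the trial's error rate is 11-14%; the documents support only the conditional statement, with its range. Nor do those figures belong to the 140 recruits: they are for the 84 expected completers.

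**Much of the excess comes from Centre B.** Caseloads are largest there, but ERP contact is lightest: an induction, a programme, then gym and classes. With the ICC at zero in Centre B, the rate falls to 7-8%. This also stands, so the Centre A-only case is shown.

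**Delivery is only partly one-to-one.** Patients use the gym, classes and daily activity options; Centre A patients may decline the 18-week programme and stay in the analysis; and nothing says one ERP sees a patient throughout. Shared patients would weaken the clustering, while unequal caseloads would strengthen it.

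**The plan uses a mixed model.** A reader might infer that it declares patients independent. It does not: its random effects are unstated. The supportable statement is that no practitioner term is specified.

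**Six to eight ERPs are too few to estimate the variance.** Correct, and a sound reason not to make a practitioner random effect the primary test. It does not justify omitting the issue.

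**Scheme is confounded with centre anyway.** True and separate. Correlation within a practitioner's caseload widens the interval further and would persist with more centres per arm.

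**Conclusion.** The point holds in conditional form. The 84 is an independent-patients figure and the analysis specifies no practitioner term, so any positive practitioner ICC makes both the 80% power and the 5% error rate too favourable.

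The size depends on an ICC that the documents do not give, on one ERP per patient and on equal caseloads. On 42 completers per arm, it ranges from slight (ICC 0.01, or clustering at Centre A only) to more than double the nominal error rate (ICC 0.05 in both arms) and beyond (0.10). If all 70 per arm contribute, the error rate at 0.05 is 15-20%.

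Two stronger conclusions are not supported. The first is that the planned model must be replaced as primary: with 2-3 ERPs at Centre B, that is a debatable trade given power of about 35-49% at ICC 0.05. The second is that a practitioner term would make the scheme comparison valid: with one centre per arm, it cannot separate scheme from centre.

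**What to change.** 1. **Process Measures, attendance at consultations.** Add a code for each patient's main ERP to the record that ERPs already complete.

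2. **Analyses.** Keep the planned model as primary. Add a pre-specified sensitivity analysis of the Group x Time contrast that allows for ERP clustering of change in the two ERS arms, with none for controls, who have no ERP. Because baseline is a level of time and is measured before the induction, the effect must be ERP x time, or an ERP effect on week-12 values adjusted for baseline; an ERP intercept alone largely cancels from Group x Time. Report the contrast and its interval at fixed ICCs of 0.01, 0.05 and 0.10, rather than relying on an estimated variance. Using the actual caseloads m_j, the arm's design effect is 1 + (sum of m_j squared / sum of m_j - 1) x ICC.

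3. **Sample size estimation.** State that 80% power assumes no ERP clustering, and give the power at those ICCs: about 75-77%, 58-64% and 44-51% with 42 per arm, and lower with small-sample degrees of freedom.

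**Cost.** One code on an existing record, one sensitivity analysis and a sentence or two of text; no extra recruitment. The price is a wider interval and a less favourable power figure. The confounding of scheme with centre is untouched and should be stated as a limitation in its own right.
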